### 8.4.5 Pregnancy

Pregnancy during the trial should be avoided and the patients must be instructed in highly effective contraception as per local guidelines (see Contraception Guidance in Appendix 4: Contraceptive Guidance and Collection of Pregnancy Information), and to use this throughout the trial through 4 weeks after receiving the last dose of trial product.

Pregnancy information for female patients and female partners of male patients will be collected after the start of trial treatment and until the follow-up visit.

If a pregnancy is reported, the Investigator should inform the Sponsor within 24 hours of learning of the pregnancy and should follow the procedures outlined in Section 10.4 (Appendix 4).

Abnormal pregnancy outcomes (e.g., spontaneous abortion, fetal death, stillbirth, congenital anomalies, ectopic pregnancy) are considered SAEs.

If a patient becomes pregnant during the trial, the patient should be withdrawn from trial (see Section 7.2).

# 8.4.6 Adverse Events of Special Interest

In this trial the following events are to be regarded as AESIs, should they occur:

- Neoplasms (malignant and benign)
- Suspicion of liver injury
- Pancreatitis
- Cholecystitis

If the event is reported as an SAE, the timelines for SAE reporting apply. If the event is reported as a non-serious AE, it should be reported in the dedicated eCRF page within 2 working days (if at all possible) of Investigator's first knowledge.

The event-specific information that needs to be captured in addition to the standard AE information is presented below:

### Neoplasms:

Information on histopathology (date of examination and results), imaging (if imaging is performed), TNM staging, history of cancer (the patient's and family), treatment received for this event, and an event narrative. Copies of images (if performed) should be stored at site. A retrospective imaging review may be performed if deemed necessary.

### **Suspicion of Liver Injury:**

Suspicion of liver injury\* is defined as:

- ALT or AST increasing more than 3 times from baseline value, or
- ALT or AST  $> 5 \times ULN$  and total bilirubin  $> 2 \times ULN$ , or
- ALT or AST  $> 5 \times ULN$  and INR > 1.5.

\* In that case, the tests should be repeated at 48-72 hours for evaluation of the event course/confirmation. Furthermore, additional information needs to be provided by the site, e.g.

physical examination, information on alcohol consumption, concomitant therapy (including herbals).

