Glepaglutide was well tolerated at daily doses of up to 10 mg in the phase 2 trial ZP1848-15073 conducted in SBS patients. Consistent with the clinical setting, the most frequently reported AEs (reported in >20% of patients) in the phase 2 trial were nausea, abdominal pain, abdominal distension, vomiting, stoma complication, fatigue, dizziness, polyuria, decreased appetite, peripheral edema and cough. Treatment-emergent serious adverse events (SAEs) comprised 8 events, with no dose dependency or clustering of events being observed. Injection site reactions were dose dependent, mild to moderate in severity and transient by nature. The most frequently reported symptoms were itching and redness. No deaths were reported in this or any other trials with glepaglutide.

No specific safety issues were raised from the phase 1 clinical trial program; for further details please see the Investigator's Brochure.

In addition to the gastrointestinal tract, there are also GLP-2 receptors in the lung, brain, and hypothalamus (22). So far, clinically significant off-intestinal targeted effects resulting from these additional receptor sites have not been seen.

Experiences with native GLP-2 and teduglutide suggest that expected common AEs for this class of compounds include abdominal pain and distension, injection site reactions, nausea, headache, upper respiratory tract infection, and (in some studies) vomiting, and fluid overload (23).

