### Medical history and concomitant diseases

- 5. More than 2 SBS-related or PS-related hospitalizations (e.g., catheter-related bacteremia/sepsis, bowel obstruction, severe water-electrolytes disturbances, etc.) within 6 months prior to screening.
- 6. Poorly controlled inflammatory bowel disease (IBD) that is moderately or severely active or fistula interfering with measurements or examinations required in the trial.
- 7. Current bowel obstruction.
- 8. Known radiation enteritis or significant villous atrophy, e.g., due to active celiac disease.
- 9. Cardiac disease defined as: decompensated heart failure (New York Heart Association [NYHA] Class III-IV), unstable angina pectoris, and/or myocardial infarction within the last 6 months prior to screening.
- 10. Clinically significant abnormal electrocardiogram (ECG) as judged by the Investigator.
- 11. Human immunodeficiency virus (HIV) positive, acute liver disease including positive results for Hepatitis B antigens (HBsAg) and Hepatitis C (HCV), or unstable chronic liver disease.
- 12. Any history of colon cancer. History of any other cancers (except margin-free resected cutaneous basal or squamous cell carcinoma or adequately treated in situ cervical cancer) unless disease-free state for at least 5 years.
- 13. Hepatic impairment defined as:
  - a. Total bilirubin  $\geq 2 \times$  the upper limit of normal (ULN), or
  - b. Aspartate aminotransferase (AST)  $\geq$  5 × ULN, or
  - c. Alanine aminotransferase (ALT)  $\geq$  5× ULN
- 14. Use of GLP-1, GLP-2, human growth hormone (HGH), somatostatin, or analogs thereof, within 3 months prior to screening.
- 15. Known or suspected hypersensitivity to glepaglutide, its components or related products.
- 16. Use of dipeptidyl peptidase (DPP)-4 inhibitors within 3 months prior to screening.
- 17. Surgical resection of gut tissue within 6 months prior to screening.
- 18. Systemic immunosuppressive therapy for treatment of the gastrointestinal tract that has been introduced or has been unstable within 3 months prior to screening.
- 19. Unstable biological therapy (e.g. anti-TNF-α, natalizumab, etc.) within 6 months prior to screening, including significant changes in doses or switch of drug.

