### 7 DISCONTINUATION OF TRIAL PRODUCT AND PATIENT WITHDRAWAL

### 7.1 Discontinuation of Trial Treatment

Treatment of a patient may be discontinued at any time during the trial at the discretion of the Investigator for safety reasons. However, the patient can still continue, and should be encouraged to stay in the trial if assessed safe according to the Investigator.

Efforts must be made so that patients continue to attend and complete all scheduled visit procedures to the extent possible. Patients should stay in the trial regardless of compliance with trial drug, assessments, or visit schedule. The Investigators should make a special effort to ensure that all patients complete the assessment for the primary and key secondary endpoints.

Patients must be educated about the continued scientific importance of their data, even if they discontinue trial product.

A patient must be discontinued from trial treatment if:

- 1. Any safety concerns or AEs that in the opinion of the Investigator might place the patient at unacceptable risk, including any deterioration of a patient's health state, especially in terms of the frequency and volume of total PS.
- 2. Any malignancy.
- 3. Increased liver values, defined as:
  - a. ALT or AST >3 times baseline value lasting more than 2 weeks\*, or
  - b. ALT or AST  $>5 \times$  ULN and total bilirubin  $>2 \times$  ULN\*, or
  - c. ALT or AST  $>5 \times$  ULN and international normalized ratio (INR) >1.5\*, or
  - d. ALT or AST  $>5 \times$  ULN with the appearance of fatigue, nausea, vomiting, right upper quadrant pain or tenderness, fever, rash, and/or eosinophilia (>5%)\*
  - \* where no other etiology exists.
- 4. Pregnancy or intention to become pregnant.
- 5. The patient requires treatment with prohibited medications (see Section 6.6).

Patients can be discontinued from trial treatment if:

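### Liver stopping criterion 3d has no counterpart in the AESI definition, so a mandatory liver stop can fall outside AESI reporting when baseline ALT/AST is above 1.67 × ULN

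*Protocol*

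**What the plan says.** **Stopping rule (Protocol Section 7.1, item 3).** Treatment must be discontinued on any of four liver criteria, each subject to the footnote "where no other etiology exists":

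- 3a: "ALT or AST >3 times baseline value lasting more than 2 weeks"
- 3b: ALT or AST above 5 × ULN with total bilirubin above 2 × ULN
- 3c: ALT or AST above 5 × ULN with INR above 1.5
- 3d: ALT or AST above 5 × ULN "with the appearance of fatigue, nausea, vomiting, right upper quadrant pain or tenderness, fever, rash, and/or eosinophilia" above 5%

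**AESI definition (Protocol Section 8.4.6).** Suspicion of liver injury has three limbs: "ALT or AST increasing more than 3 times from baseline value", and two limbs that match 3b and 3c. It has no symptom limb and no etiology condition. Meeting the definition brings a dedicated eCRF page within 2 working days if non-serious, a repeat test at 48-72 hours, and a structured narrative.

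**Entry limit (Protocol Section 5.2, criterion 13).** Under "Hepatic impairment defined as", patients are excluded at ALT or AST of 5 × ULN or more, or total bilirubin of 2 × ULN or more. Lower values are admitted.

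**Retest elsewhere.** Sections 8.3.5 and 8.11 also call for a 48-72 hour repeat when liver injury is suspected from raised ALT, AST, ALP or total bilirubin. Section 8.3.5 refers back to 8.4.6 at that point.

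**SAP.** Section 4.4 and Appendix B (Listing 3-2) list AESIs. AEs leading to permanent discontinuation are tabulated and listed separately (Table 3-1.5, Listing 3-5).

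**The concern.** The liver criteria that end treatment would be expected to sit inside the set that triggers special-interest reporting. Here one of them does not. Suspicion of liver injury is one of four AESIs in a trial without a Data Monitoring Committee, and the extra information depends on meeting the 8.4.6 definition.

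The narrative matters most. It is where alcohol use, concomitant therapy and herbals are to be described, and so where the no-other-etiology judgement behind a stop would be documented in a structured way. It also asks for nausea, vomiting, fever, rash and abdominal tenderness, which largely overlap with the 3d symptoms, so the omission looks inadvertent.

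A second, smaller problem is wording. Section 7.1 sets a multiple of the baseline value, while Section 8.4.6 speaks of an increase from baseline. The latter can be read as a rise of more than 3 times, which puts the threshold at 4 times baseline.

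**Working it through.** No sample size or power figure bears on this point. The check compares thresholds. All values are multiples of ULN: *b* is baseline ALT or AST, *x* the on-treatment value. From criterion 13, *b* < 5.

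**Step 1. Criteria side by side, reading AESI limb 1 as *x* > 3*b*.**

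| Section 7.1 item 3 | Section 8.4.6 | Relation |
|---|---|---|
| 3a: *x* > 3*b* for more than 2 weeks | Limb 1: *x* > 3*b*, no duration | AESI wider |
| 3b: *x* > 5 and bilirubin > 2 | Limb 2: same | Same thresholds |
| 3c: *x* > 5 and INR > 1.5 | Limb 3: same | Same thresholds |
| 3d: *x* > 5 with symptoms or eosinophilia | None | Gap |

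The etiology condition applies to all stopping criteria and to no AESI limb, which makes the AESI side wider again for 3a to 3c.

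**Step 2. When 3d is met without an AESI.** All of these must hold: *x* > 5, *x* ≤ 3*b*, bilirubin ≤ 2, INR ≤ 1.5, a 3d symptom or eosinophilia, and no other etiology. The first two are compatible only if 3*b* > 5, that is *b* > 5/3 = 1.67.

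| Baseline (× ULN) | 3 × baseline | Range of *x* in the gap |
|---|---|---|
| 1.00 | 3.0 | none |
| 1.67 | 5.0 | none |
| 2.0 | 6.0 | above 5, up to 6 |
| 3.0 | 9.0 | above 5, up to 9 |
| 4.0 | 12.0 | above 5, up to 12 |
| 4.9 | 14.7 | above 5, up to 14.7 |

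Since *b* < 5, the upper end stays below 3 × 5 = 15. At *b* ≤ 1.67, any value above 5 already exceeds 3 times baseline and is an AESI. Enumerating baselines from 0.20 to 4.95 in steps of 0.05 against values from 0.2 to 20 gave the same picture: 3d was the only stop that escaped, for grid baselines 1.70 to 4.95.

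**Step 3. Reading limb 1 as a rise of more than 3 times, so *x* > 4*b*.** The 3d gap then starts at *b* > 5/4 = 1.25. In addition, 3a stops with *x* above 3*b* but not above 4*b* can escape.

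**Step 4. Entry limit.** At entry *x* = *b* < 5, so neither *x* > 3*b* nor *x* > 5 holds. No eligible baseline meets a stopping or AESI limb.

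**The case against.** The strongest reply is that little is lost. The primary reason for stopping goes into the eCRF (Section 7.1), and clinically relevant laboratory changes are recorded as AEs (Section 8.3.5). The Safety Committee's sources include all AEs and laboratory parameters (Section 10.1.6). The SAP tabulates AEs leading to discontinuation and lists liver values by patient, including those from unscheduled visits. With at most 16 patients, a reader of the listings would find the event. This stands, and it confines the loss to the AESI page with its timeline, the structured narrative and the AESI listing.

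Several stronger readings are tempting, but the documents do not support them:

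- *The AESI definition is narrower than the stopping rule overall.* It is narrower only for 3d. With limb 1 read as 3 times baseline, it matches the thresholds of 3b and 3c and is wider than 3a.
- *Both rules clash with the entry limit.* Step 4 shows they do not. The entry limit matters only because it admits the baselines at which the gap exists.
- *A patient entering at 4.9 × ULN is stopped by a 2% rise plus nausea.* This ignores the etiology condition and the requirement that symptoms appear.
- *No retest would follow.* Sections 8.3.5 and 8.11 call for one, and 8.3.5 also requires clinically significant abnormal values to be repeated. What remains open is whether a 3d-only event counts as suspected liver injury, given the reference back to 8.4.6.
- *Very low baselines give alerts within the normal range, so the rule is wrong.* That follows from any baseline-relative rule and is not a contradiction.

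Raised baselines are plausible, since Section 2.2 names liver damage as a complication of parenteral support. The documents give no baseline enzyme distribution, however, and exclusion criterion 11 removes acute and unstable chronic liver disease.

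**Conclusion.** The point holds as a gap in reporting. An eligible patient with baseline ALT/AST above 1.67 and below 5 × ULN can meet mandatory stopping criterion 3d without meeting the AESI definition. The on-treatment value lies above 5 × ULN and at or below 3 times baseline, with bilirubin at most 2 × ULN and INR at most 1.5. The event would not require the AESI page or liver narrative and would be missing from the AESI listing. It would still appear as a discontinuation reason, in the laboratory listings, and among AEs leading to discontinuation if recorded as an AE.

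This assumes that the baseline used is below the entry limit, that no other etiology is found, and that the event is not also serious (SAE reporting would then apply). It takes the 8.4.6 multiple as 3 times baseline; under the alternative reading the gap is larger. How often it would occur among 6 to 16 patients cannot be estimated from the documents, and few events are likely. No view is taken on which thresholds are clinically right.

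**What to change.** Reconcile Protocol Sections 7.1 (item 3), 8.3.5, 8.4.6 and 8.11 so that:

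- every liver event meeting a Section 7.1 item 3 stopping criterion is also captured by the AESI reporting definition;
- the baseline multiple is worded identically in 7.1 and 8.4.6;
- it is explicit whether the 48-72 hour retest covers a 3d-only event.

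This aligns reporting with stopping. Any change to thresholds is for the sponsor's hepatic safety experts.

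Optionally, add one SAP table of patients meeting each liver criterion at any time, including unscheduled retests, which SAP Section 2.1.1.2 confines to listings.

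The cost is amendment wording, one eCRF trigger, a few more AESI narratives and, if adopted, one table.

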### Narrative of the event should include:

- Clinical signs and symptoms and how they developed over time. Aspects like e.g.
  abdominal pain, nausea, vomiting, jaundice, fever, rash, abdominal tenderness,
  hepatomegaly, splenomegaly, blood pressure, peripheral edema, jugular venous
  distension, signs of ascites, recent weight gain should be considered and described.
- Information on relevant medical history, alcohol consumption, and relevant concomitant therapy (including herbals).
- Lab tests (at local lab, if needed): as a minimum ALT, AST, Bilirubin (direct and total) and INR. Other tests may be warranted as clinically indicated.
- Imaging diagnostic (ultrasound/CT scan/MRI/Other imaging modality). Copies of images (if performed) should be stored at site.
- Biopsy results (if performed).

### Pancreatitis:

# Narrative of the event should include:

- Clinical signs and symptoms and how they developed over time. Aspects like pain (character of the pain including the anatomical region (e.g. sudden and in center abdomen) +/- irradiating pain in the back), tenderness of the abdomen, diarrhea, indigestion, fever, jaundice) should be considered and described.
- Information on relevant medical history, alcohol consumption, and relevant concomitant therapy (including herbals).
- Lab tests (at local lab, if needed): pancreatic and liver function tests, including lipase, amylase, ALT, AST, bilirubin, and ALP. Other tests may be warranted as clinically indicated.
- Imaging diagnostic (ultrasound/CT scan/MRI/Other imaging modality). Copies of images (if performed) should be stored at site.
- Biopsy results (if performed).

### **Cholecystitis:**

### Narrative of the event should include:

- Clinical signs and symptoms and how they developed over time. Aspects like pain (character of the pain including the anatomical region (e.g. sudden, after a large meal, in upper right or center abdomen) +/- irradiating pain to right shoulder or back), tenderness of the abdomen, nausea, vomiting, and fever should be considered and described.
- Information on relevant medical history, alcohol consumption, and relevant concomitant therapy (including herbals).
- Lab tests (at local lab, if needed): liver function tests, including ALT, AST, bilirubin, and ALP. Other tests may be warranted as clinically indicated.
- Imaging diagnostic (ultrasound/X-Ray/CT scan/MRI/Other imaging modality). Details like presence of gall bladder stones and common bile duct diameter should be reported, if available.

# **8.4.7** Other Important Events

The following events must always be reported to Pharmalex according to SAE timelines, regardless of whether the event is non-serious or serious:

- Suspicion of transmission of infectious agents via the trial product.
- Overdose of the trial product.
- Medication error involving the trial product.
- Inadvertent or accidental exposure to the trial product.

Note: Medication errors are defined as all unintended failures (e.g. wrong kit, missing dose, not taking the full amount, etc.) to administer the investigational product correctly that either:

- Lead to harm to the patient
- Have the potential to lead to harm to the patient

Other important events must be recorded in the eCRF.

### **8.4.8** Technical Complaints

Technical complaints on trial products and technical issues with the device will be reported by the Investigator via the eCRF.

### 8.4.9 Precautions

Normal precautions taken for a human trial, including the provision of emergency equipment, will be taken during this trial. Qualified and well-trained physicians and medical staff will instruct the patients. During a patient's participation in the trial, the Investigator should ensure that adequate medical care is provided to the patients for any AEs, including clinically significant laboratory values related to the trial. The Investigator should inform the patient when medical care is needed for intercurrent illnesses of which the Investigator becomes aware.

For further information on safety precautions for glepaglutide, refer to the current version of the Investigator's Brochure.

### **8.5** Treatment of Overdose

The Sponsor does not recommend specific treatment for an overdose.

In the event of an overdose, the Investigator should:

- Contact the Medical Monitor immediately.
- Closely monitor the patient for any AE/SAE and laboratory abnormalities for at least 14 days. In case of AEs/SAEs, these should be followed up until resolution, stabilization or until the event is otherwise explained, or the subject is lost to follow-up as described in section 8.4.3.
- Document the quantity of the excess dose as well as the duration of the overdose in the eCRF.

Decisions regarding dose interruptions or modifications will be made by the Investigator in consultation with the Medical Monitor based on the clinical evaluation of the patient.

### 8.6 Pharmacokinetics

PK parameters will be assessed as an exploratory endpoint.

Blood samples for assessment of PK will be taken according to Table 3, and prior to administration of trial product at other visits (if dosing occurs on the visit day). Details are provided in the laboratory manual. The actual date and time of each sample will be recorded. The PK sampling schedule is set in order to be able to correlate PK values of glepaglutide to ADA data and to obtain sufficient information from the dosing regimen tested. Results will not be revealed to the site. PK samples will be shipped for analysis to Charles River Laboratories, UK. Samples will be destroyed after completion of the final clinical trial report.

# 8.7 Pharmacodynamics

Pharmacodynamic parameters are not evaluated in this trial.

### 8.8 Genetics

Genetics are not evaluated in this trial.

### 8.9 Biomarkers

Biomarkers are not evaluated in this trial.

### 8.10 Health Economics

Health Economics parameters are not evaluated in this trial.

### 8.11 Unscheduled Visits

If required an unscheduled visits can be performed, including, but not limited to, any of the following:

- PS volume adjustments
- Lab sampling: In case of suspected liver injury based on increased ALT, AST, ALP, or total bilirubin, the tests should be repeated at 48-72 hours for evaluation of the event course/confirmation
- Additional trial product dispensing and/or to replace trial product to ensure that no patient use expired trial product at any time

### 9 STATISTICAL CONSIDERATIONS

# 9.1 Statistical Hypotheses

The primary statistical null hypothesis  $H_0$  is defined as

 $H_0$ : mean 24-week change in Wet Weight Absorption = 0

With the alternative hypothesis being defined as

 $H_a$ : mean 24-week change in Wet Weight Absorption  $\neq 0$ 

For the key secondary endpoint the corresponding null hypothesis is defined as

 $H_0$ : mean 24-week change in absorption of energy = 0

With the alternative hypothesis being defined as

 $H_a$ : mean 24-week change in absorption of energy  $\neq 0$ 

The statistical hypotheses will be tested sequentially in a hierarchical testing procedure, such that the rejection of the primary hypothesis leads to the test of the secondary hypothesis, whereas the acceptance of the primary hypothesis prevents confirmatory testing of the secondary null hypothesis. In addition to the primary and secondary hypotheses, supplementary analyzes will be performed that analyze the primary hypotheses for the SBS-II and SBS-IF patients separately. The supplementary analyzes will however not be part of the testing strategy.

# 9.2 Sample Size Determination

Sample size is planned based on both, feasibility considerations and statistical considerations. Sample size should be such that there is sufficient power to reject at least the primary null hypothesis (primary endpoint). In the phase 2 trial, ZP1848-15073, after three weeks of treatment, the pooled 1 and 10 mg/day treatment groups displayed a mean (SD) change from baseline in absorption of wet weight fluids of 719 g/day (340 g/day), corresponding to an effect size (mean divided by standard deviation) of 2.11. Calculations based on a one-sample t-test (alpha= 0,05, two-sided) reveal 90% power for a statistically significant test result of the primary null hypothesis, if an effect size of 2.11 can be assumed and 5 patients are analyzed. The effect size is the true population mean of the 24 week change in wet weight absorption divided by its standard deviation.

In the same trial, the change from baseline in the intestinal energy absorption was 391 KJ/day (1374 KJ/day), corresponding to an effect size of 0.28. While achieving statistical significance for the key secondary endpoint in addition to the primary endpoint is aimed for, a sample size providing high power for the key secondary endpoint is not considered feasible, should a similar variability have to be expected for the present study. It seems, however, reasonable to assume that the variability of results for the key secondary endpoint will be lower after 24 weeks compared to after 3 weeks. Should the reduced variability lead to an effect size of around 1.15, then the below table shows that 90% power can be achieved with 10 patients in the analysis, and 80% power can be achieved with 8 patients in the analysis. Even a less extensive reduction in variability can still lead to a reasonable power with 8 to 10 patients in the analysis.

| Number Of Patients | Effect Size | Power (%) |
|---------------------------|-------------|-----------|
| 8                         | 1,156       | 80        |
| 8                         | 1,2         | 82        |
| 8                         | 1,3         | 88        |
| 8                         | 1,342       | 90        |
| 8                         | 1,4         | 92        |
| 10                        | 0,996       | 80        |
| 10                        | 1,0         | 80        |
| 10                        | 1,1         | 87        |
| 10                        | 1 155       | 00        |

Table 9 Power calculation of a One-Sample t-test for different effect sizes

Taken together, the sample size will be as follows: Aiming for at least 8 patients in the full analysis set (i.e. patients assigned to trial treatment who received at least one dose), 2 more patients will be allocated to treatment. This means patients will be screened until 10 eligible patients (eligible with respect to inclusion and exclusion criteria) are enrolled and allocated to treatment. Patients with SBS-II and SBS-IF will be included in the trial, with an aim of an equal distribution between the two.

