#### **Number of Patients**

A minimum of 6 and a maximum of 16 patients are planned to be enrolled in the trial (see Section 9.2). Patients with SBS-II and SBS-IF will be included in the trial, with an aim of an equal distribution between the 2 groups (see Section 5). A screen failure rate of 10% is expected, hence, a maximum of approximately up to 18 patients are expected to be screened.

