#### 4 TRIAL DESIGN

# 4.1 Overall Design

This is a single-center phase 3b trial investigating the long-term effect on intestinal absorption and nutritional status and long-term safety of treatment with glepaglutide in patients with SBS.

It is planned to enroll a minimum of 6 and a maximum of 16 patients for the trial, where enrollment is defined as receiving trial product.

The overall trial design is presented in Figure 1.

The orange circles represent 48-hour in-house metabolic balance studies. Visits are indicated with lines and the week number from Visit 1 is indicated.

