#### 5.4 Screen Failures

Screen failures are defined as participants who consent to participate in the clinical trial but are not subsequently assigned to trial intervention. A minimal set of screen failure information is required to ensure transparent reporting of screen failure participants to meet the Consolidated Standards of Reporting Trials (CONSORT) publishing requirements and to respond to queries from regulatory authorities. Minimal information includes demography, screen failure reason(s), eligibility criteria, and any SAE. A screen failure rate of 10% is expected.

Individuals who do not meet the criteria for participation in this trial (screen failure) may be rescreened. Rescreened participants should be assigned a new participant number for every screening/rescreening event.

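### The protocol plans 6 to 16 patients in two places and 10 in Section 9.2, and it counts the target of 8 in the full analysis set rather than in evaluable patients

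*Protocol*

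**What the plan says.** The current protocol text gives the planned number in three places.

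- **Synopsis, Number of Patients:** "A minimum of 6 and a maximum of 16 patients are planned to be enrolled in the trial (see Section 9.2"). With a 10% screen failure rate it adds that "a maximum of approximately up to 18 patients are expected to be screened".
- **Section 4.1:** "It is planned to enroll a minimum of 6 and a maximum of 16 patients for the trial". The same sentence fixes what counts as enrolled: "where enrollment is defined as receiving trial product".
- **Section 9.2:** the starting point is "Aiming for at least 8 patients in the full analysis set (i.e. patients assigned to trial treatment who received at least one dose"). As an allowance on top of that 8, "2 more patients will be allocated to treatment". The recruitment rule drawn from these two figures is that "patients will be screened until 10 eligible patients (eligible with respect to inclusion and exclusion criteria) are enrolled and allocated to treatment".

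Section 5.4 repeats the rate: "A screen failure rate of 10% is expected". Section 9.2 states key secondary power for patients in the analysis, namely 80% with 8 and 90% with 10 if the effect size is around 1.15. Table 9 has rows for 8 and 10 patients only.

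On who enters the test, protocol Section 9.4.1 and SAP Section 2.2.3 use observed data without replacing missing values. SAP Section 4.3.1 averages over patients who have data. Protocol Section 7.2.1 rules out replacing patients. SAP Section 2.2.1 requires both 24-hour periods of a balance study for a patient on parenteral support. The SAP as supplied states no sample size.

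**The concern.** Two things do not fit together.

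**The number.** Section 9.2 sets a stopping target of 10. The other two places allow stopping at 6, which is below Section 9.2's own target of 8, or continuing to 16. The synopsis points to Section 9.2 for its range, and Section 9.2 does not contain it. A reader of the final report could not tell whether a trial that ended with 6 or with 16 patients had followed its plan.

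**The counting unit.** Power depends on how many patients supply a change from baseline to Week 24. The full analysis set requires only one dose. Under the Section 4.1 definition an enrolled patient has already been dosed, so 10 enrolled are 10 in that set. The 2 extra patients then add nothing to a target of 8 counted there. They give cover only if the 8 means patients with usable balance studies at both visits.

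The endpoint affected is energy absorption, the second and last test in the confirmatory hierarchy. Section 4.2 expects the energy data to contribute to the regulatory filing.

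**Working it through.** **Inputs (protocol Section 9.2 unless noted).** One-sample t-test, two-sided alpha 0.05. Primary effect size 719/340 = 2.11. Key secondary effect size about 1.15 (assumed in the protocol; the phase 2 value was 391/1374 = 0.28). Screen failure 10% (synopsis and Section 5.4).

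**Formula.** With n patients in the test and effect size d, the statistic is noncentral t with n − 1 degrees of freedom and noncentrality d√n. Power is the probability that it falls outside ±t(0.975, n − 1).

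**Step 1: reproduce the plan's figures.**

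| n | Effect size | Stated | Computed |
|---|---|---|---|
| 8 | 1.156 | 80% | 80.0% |
| 8 | 1.2 | 82% | 82.8% |
| 8 | 1.3 | 88% | 88.2% |
| 8 | 1.342 | 90% | 90.0% |
| 8 | 1.4 | 92% | 92.2% |
| 10 | 0.996 | 80% | 80.0% |
| 10 | 1.0 | 80% | 80.3% |
| 10 | 1.1 | 87% | 87.1% |
| 10 | 1.155 (row damaged in the extracted text) | 90% | 90.0% |

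Table 9 is sound. For the primary endpoint, 5 patients give 93.3% against the stated 90%. Since 4 give 79.4%, 5 is the smallest number that reaches 90%, so the statement reads as at least 90%.

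**Step 2: which plan the screening number follows.** Screened = enrolled/(1 − 0.10).

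- 16/0.9 = 17.8, so 18, as the synopsis states.
- 10/0.9 = 11.1, so about 12.

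The screening figure belongs to the 6 to 16 plan.

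**Step 3: key secondary power at effect size 1.15, by number in the test.**

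| n | t critical | 1.15√n | Power |
|---|---|---|---|
| 6 | 2.571 | 2.817 | 61.9% |
| 7 | 2.447 | 3.043 | 71.9% |
| 8 | 2.365 | 3.253 | 79.6% |
| 10 | 2.262 | 3.637 | 89.8% |
| 16 | 2.131 | 4.600 | 99.0% |

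If 8 is met only as a count of dosed patients, one without evaluable data leaves 7 (72%) and two leave 6 (62%). If 10 are dosed and 2 are not evaluable, 8 remain and the stated 80% holds.

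**Step 4: primary power at effect size 2.11.** n = 6: 98.2%. n = 8: 99.9%. n = 10 and n = 16: above 99.9%.

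**Step 5: the sentence on a smaller fall in variability.** Section 9.2 says that a less marked reduction can still give reasonable power with 8 to 10 patients. Table 9 supports this at n = 10, down to an effect size of about 1.0 (80%). It has no row below 1.15 at n = 8. There the values are 76.1% at 1.1 and 68.1% at 1.0.

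**The case against.** **Ten lies inside 6 to 16**, so a target within wider bounds is not an arithmetical contradiction. That is correct. But the text does not present 10 as a target within bounds: the lower bound falls below Section 9.2's own target of 8, the cross-reference leads to text without the range, and the screening number was derived from 16 alone.

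**Section 9.2 read by itself is coherent**, as 10 allocated so that 8 receive a dose. This also has force. It fails once Section 4.1 equates enrolment with dosing, because Section 9.2 continues until 10 are both enrolled and allocated. The likely intent is 8 evaluable patients, but the text says otherwise.

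**Week 24 data are already protected.** Section 7.1 keeps patients who stop treatment in the trial and asks for special effort on the primary and key secondary assessments. Section 8.1.7 lets Visit 9 be postponed under the pandemic provisions. These measures make losses less likely; they do not change what is counted.

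**Stronger readings that the documents do not support:**

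- A reader might infer that the protocol claims adequate key secondary power across 6 to 16. It claims power only at 8 and 10, sizes the trial on at least the primary hypothesis, and concedes that high key secondary power is not feasible at phase 2 variability.
- A reader might infer that the sentence on a smaller fall in variability is baseless. Table 9 backs it at n = 10, the protocol does not define reasonable power, and the effect size of 1.15 is stated conditionally.
- A reader might infer either that type I error is inflated or that it is certainly unaffected. Nothing says that the final number would depend on results, but no rule in this open-label trial excludes it either. Neither conclusion is established.

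**Conclusion.** The point holds as an inconsistency in the planned size and in the counting unit. It is not a failure of the power calculation, whose figures reproduce. It is worth correcting because the sample size is a figure against which the trial will be judged.

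The consequence is confined to the key secondary endpoint. The stated 80% with 8 becomes 72% with 7 evaluable patients and 62% with 6. The primary endpoint keeps 98% power even with 6.

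These key secondary figures rest on the protocol's assumed effect size of 1.15; at the phase 2 value of 0.285, power is only 10.8% with 8 and 12.7% with 10. The primary figures rest on the phase 2 effect size of 2.11 carrying over to Week 24. The documents give no expected rate of non-evaluable patients, so the losses of one and two are illustrations, not forecasts.

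**What to change.** Protocol wording only; no added patients and no change to the analysis.

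1. **Reconcile the synopsis, Section 4.1 and Section 9.2.** There are two ways:
   - State one size in all three. If it is 10, change the 18 screened to about 12.
   - Keep 6 to 16 in all three. Add to Section 9.2 a rule for choosing within the range that does not depend on efficacy results, and give power at both ends: key secondary at effect size 1.15, 62% with 6 and 99% with 16; primary, 98% with 6 and above 99.9% with 16.
2. **Define the target of 8** as full analysis set patients with evaluable balance studies at Visits 1 and 9, and say that the 2 extra patients cover those who are not evaluable.
3. **Optional.** Keep the sentence on a smaller fall in variability, but tie it to n = 10, where Table 9 supports it down to an effect size of about 1.0. Alternatively, add rows for n = 8 (1.1: 76%; 1.0: 68%).

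The only cost is that, if the range is kept, the protocol must show the 62% at its lower end.
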